6.5 N/A

6.6 N/A

7.0 Data and Specimen Banking* N/A

N/A

8.0 Sharing of Results with Participants*

8.1 Study-related assessment and treatment results may be shared with participants upon request, without clinical interpretation.

8.2 N/A

8.3 N/A

8.4 N/A

9.0 Study Timelines*

9.1 Participants will complete the study in approximately 7 weeks. We anticipate an active recruitment period of 1.5 years with all study procedures completed by end of 2023.

10.0 Inclusion and Exclusion Criteria*

10.1 Individuals who indicate interest in participating will undergo a brief phone screen to determine if they meet the initial eligibility criteria. Contact will be via telephone to prevent unnecessary burden of traveling to the Atlanta VA if the individual does not qualify for the study. Subjects will be informed of the nature of the study and procedures and their right not to participate.

10.2 Inclusion criteria: Participants will be: 1) 18-89 years of age; 2) ≥ 1 month post-stroke; 3) proficient English speakers; 4) of moderate functional disability (17-67 scored on Functional Independence Measure, observational (Granger et al. 1993) or telephone-administered (FONE-FIM; Chang, Slaughter, et al. 1997; Chang, Chan, et al. 1997) as indicated by published ranges (Chumney et al. 2010); 5) experiencing aphasia as determined by a Western Aphasia Battery Aphasia Quotient of <93.7 (Kertesz, 1982) and memory impairment as determined by a score that is >1.5 standard deviations below the norm on the Brief Visuospatial Memory Test- Revised (Benedict et al. 1996), the Hopkins Verbal Learning Test- Revised (Benedict et al. 1998) or digit span forward and backward (Lezak et al., 2004); and 6) able to provide informed consent to participate, using aphasia-accessible process, as needed.

Exclusion criteria: History of brain conditions other than left brain stroke, including clinical right brain pathology.

10.3 N/A

10.4 N/A

11.0 Vulnerable Populations* N/A

11.1 N/A

12.0 Local Number of Participants

12.1 30

12.2 Based on attrition rates in our previous studies, we expect ~20% of participants will not complete the study. Thus, we will need to enroll approximately 36 participants to achieve the target sample size of 30. We anticipate needing to screen approximately 100 patients in order to meet our target sample size.

13.0 Recruitment Methods

13.1 This study will target United States Veterans. Non-VA patients maybe enrolled to maximize the number of women in the study as historically difficult to enroll enough women. Our primary recruiting sources will be the VA Clinical Case Registry (CCR) using selected ICD-9 and ICD-10 codes. Potential Veteran participants will be mailed an IRB approved recruitment letter, as well as an opt in/opt out response form to be returned using a postage paid envelope. This will allow for potential subjects to indicate whether they would like to be contacted in the future related to the study. If no response is received within two weeks, we will follow up with a phone call to gauge subject interest. The potential participants that do not meet the screening criteria for this study will be offered the option to enroll in the Atlanta VA Rehab R&D CVNR Participant Registry (IRB00000159), a secure electronic list of people who wish to be told about the research studies at the CVNR. We will also recruit through the CVNR Research Registry (IRB#00000159), referrals from VA healthcare providers, and advertisements in clinics and closed-circuit television at the Atlanta VA Health Care System. As it is estimated that only 20% of Veterans with aphasia receive their healthcare within the VA Health Care System (VAntage Point, 2018), Emory Healthcare is also an important recruitment source for Veterans. Our recruitment network at Emory includes the Emory Stroke Team that includes members of the Emory-Georgia Stroke Network and the Marcus Stroke & Neuroscience Center at Grady Memorial Hospital, which together serve approximately 750 new stroke patients yearly. Recruitment will also be supported by community-based advertisement through online and in person distribution of approved recruitment materials via professional organizations such as the Georgia Speech-Language-Hearing Association (GSHA), the American Speech-Language-Hearing Association (ASHA), and Up Close Marketing, Inc.

13.2 Participants will be recruited from the sources described in 13.1.

13.3 Methods used to identify potential participants include clinical and research registries described in 13.1, referrals from providers, review of medical records and study fliers.

13.4 We will use study fliers to assist with recruitment.

13.5 Participants will receive \$15 per session. Payments will be disbursed at completion of the study or at the point of termination or withdrawal.

14.0 Withdrawal of Participants*

14.1 Participants will be withdrawn from the study if they do not follow study procedures or if continuing in the study would be unsafe.

14.2 Terminations will be communicated promptly with the participant and compensation for completed study visits will be processed.

14.3 Data collection will not continue with participants who withdraw from the study, but data already collected may be used.

15.0 Risks to Participants*

15.1 Language and cognitive assessment: Subjects may become worried if they fail to meet cognitive screening criteria. This risk is only occasional, and effects are manageable by study staff who will be administering the tests. Subjects may become frustrated during cognitive and language tests. This risk is only occasional and effects are manageable by study staff who will be administering the tests. Subjects may become fatigued during cognitive and language tests. This risk is only occasional and effects are manageable by study staff who will be administering the tests. Additionally, we will decrease testing burden for participants, when possible. [name] study entitled "Intention Treatment for Anomia" (IRB#116056) also investigates stroke and aphasia. While the question for this study is different, the framework is in place to use assessment data collected in [name] other study to reduce the number of assessments in this study. Specifically, we may obtain a participant's data on the Western Aphasia Battery-Revised (WAB-R), Hopkins Verbal Learning Test-Revised (HVLT-R), Brief Visuospatial Memory Test-Revised (BVMT-R), and Digit Span.

Nausea due to prism adaptation goggles: Some subjects may experience nausea while wearing the prism adaptation goggles. This risk is minimal and expected to resolve after removal of the goggles. However, per the treatment manual, we will administer the Nausea Profile the first three days of treatment and discontinue if nausea persists. The nausea profile is found on pg 15 of the treatment manual.

Loss of confidentiality: There is a risk that a subject's identifiable information (PHI, PII) will be inadvertently seen by someone other than study personnel who are authorized to access the information. Loss of confidentiality can occur during language and cognitive testing. This risk is minimal and will be managed by adhering to guidelines set forth to maintain confidentiality.

15.2 There may be risks to participants that are currently unforeseeable.

15.3 N/A

15.4 N/A

16.0 Potential Benefits to Participants*

16.1 Participants will receive information about their language, memory, spatial and physical abilities, functional abilities and pain.

16.2 There may be no direct benefit to study participation.

17.0 Data Management* and Confidentiality

17.1 Data on four key areas of feasibility will be analyzed using descriptive statistics, including measures of frequency, central tendency, dispersion and variation. See Table above.

17.2 Study staff will complete and stay current on all training regarding data security and confidentiality. Written and electronic data will be coded by subject number. All written data will be kept in study binders or folders in a locked cabinet in the PI's locked office. Electronic data containing any identifiable information (PHI, PII), including audio and video recordings, will be kept in a VA protected environment (e.g., VA-approved servers). Audio and video recordings obtained on VA-approved devices will be transferred to a VA-approved server using a VA-issued USB device.

17.3 Checklists will be used to ensure that all study procedures are completed. Reliability checks will be completed on data from assessments.

17.4 Describe how data or specimens will be handled study-wide: All data will be stored on the VA trusted server. Data will be stored in closed systems with access only for study team members on VA trusted server. Identifiable data will only be stored for the length of the study plus any unanticipated delay time. If data is retained after this time it will be de-identified. Study team members will have access to the data. The PI is ultimately responsible for the receipt of the data and storage to the appropriate locations. Data will not be transported as it will be stored to the appropriate online storage from its collection point.

18.0 Provisions to Monitor the Data to Ensure the Safety of Participants*

N/A

19.0 Provisions to Protect the Privacy Interests of Participants

19.1 Confidentiality will be protected throughout the study and following completion of the study. All study participants will receive a Subject ID which will be kept separate from all source documents. As a guard against risk of confidentiality, all information will be stored in locked files in a locked research area that can only be accessed by research personnel. No names or identifying information will be used in publications that result from this research. In cases where data are laptop, no data containing identifiers or PHI will be stored on hard drives—only on removable media, which will be removed from the computer when not in use. All databases will be password protected.

19.2 Study procedures will be explained to the participant during informed consent, and at the beginning of each study visit. Participants will regularly be

asked if they have any questions and reminded that they can opt out of the study at any time.

19.3 All participant data will be stored on VA Research Server and only approved study team members will have access to this data.

19.4 Study staff will access data through VA approved networks.

20.0 Economic Burden to Participants

20.1 Participants will pay for the cost of traveling to and from study visits. We provide compensation of \$15 per visit to help defray these costs.

21.0 Consent Process

The informed consent process may be conducted face-to-face or by VA-approved audio (phone) or video communication to decrease the amount of face-to-face interaction at the Atlanta VA. For face-to-face orientation and consent, the PI/Co-PI or their trained study staff will go over and describe the consent in a quiet room. Prior to providing written consent, potential subjects will be given the chance to ask questions and the PI/Co-PI or study staff will ask questions to ensure the potential subject understands what the study entails. For phone or video consenting, we will mail or email through VA Outlook using Azure encryption two unsigned copies of the ICF/HIPAA. We will ensure the individual has enough time after receiving the document to read it before scheduled phone/video call. Trained staff will perform consenting process including speaking with the individual to discuss the study and highlighting each section of the consent form, allowing the participant an opportunity to ask questions before providing consent, and giving the participant enough time to consider being in the study. Study team will inform the individual that if they would like to take more time to consider the study, another telephone call can be scheduled. If the individual would like to participate, the participant will sign and date the document and return it to study team via mail (phone) or via email to your VA Outlook email address (video). Recordings of the audio or visual communication will not be permitted. Study team will write a “Note to File” that documents everything about the interaction including: 1. When and how the consent form was sent 2. When the video/telephone call was made 3. What was discussed during the call 4. When the signed consent form was received 5. When the signed consent form was signed by the person obtaining consent 6. When a copy of the consent form signed by both subject and study team was given to the participant and 7. A description of why signature dates are different (if applicable). Once the study team receives the signed consent form, the person obtaining consent should sign the form and date it for the day it was signed. Study procedures will begin once the signed copy is received. Text messages may be used by the study team to communicate with subjects who have consented to participate. All text messages will be sent using an encrypted, VA-issued study iPhone. A copy of the fully signed consent form will be given to the participant via mail or in person at next scheduled visit. Prior to any virtual study visits, a

technology questionnaire will be completed to determine if the participant will be able to complete any study procedures virtually. Please describe:

Non-English-Speaking Participants N/A

N/A

Waiver or Alteration of Consent Process (consent will not be obtained, required information will not be disclosed, or the research involves deception)

N/A

Participants who are not yet adults (infants, children, teenagers) N/A

N/A

Cognitively Impaired Adults N/A

N/A

Adults Unable to Consent N/A

N/A

22.0 Process to Document Consent in Writing

22.1 Participants will provide written informed consent.

22.2 N/A

22.3 Document for obtaining written consent available in IRB smart form.

23.0 Setting

23.1 All study visits will take place at Center for Visual and Neurocognitive Rehabilitation (CVNR), Atlanta VA Health Care System. The study staff will identify and recruit potential participants as outlined in section 13.0.

24.0 Resources Available

24.1 Our primary recruiting sources will be the VA Clinical Case Registry (CCR) using selected ICD-9 and ICD-10 codes, CVNR Research Registry (IRB#00000159), referrals from VA healthcare providers, and advertisements in clinics and closed-circuit television at the Atlanta VA Health Care System. As it is estimated that only 20% of Veterans with aphasia receive their healthcare within the VA Health Care System (VAntage Point, 2018), Emory Healthcare is also an important recruitment source for Veterans. Our recruitment network at Emory includes the Emory Stroke Team that includes members of the Emory-Georgia Stroke Network and the Marcus Stroke & Neuroscience Center at Grady Memorial Hospital, which together serve approximately 750 new stroke patients

yearly. Approximately 40% of individuals with left hemisphere stroke present with aphasia, and our recruitment target is 30. We anticipate we will need to screen about 100 people to reach our enrollment target. Screening and enrollment will occur on a rolling basis with PI and staff time dedicated to recruitment. Our facility contains quiet rooms for obtaining informed consent, as well as administering assessments and treatment. Study funds will be used to obtain all necessary materials for completing study procedures. The PI and other study staff are trained in all study-related procedures and will stay current on mandatory trainings related to human subjects research. A signed statement of study roles and responsibilities, along with training certificates, will be kept on file.

25.0 Multi-Site Research when Emory is the Lead Site*N/A

N/A

Widar, M., and G. Ahlstrom (2002). Disability after a stroke and the influence of long-term pain on everyday life. Scand J Caring Sci, 16, 302-10.

Wilson, B., J. Cockburn, and P. Halligan (1987). Development of a behavioral test of visuospatial neglect. Archives of Physical Medicine and Rehabilitation, 68, 98-102.

Winstein, C. J., J. Stein, R. Arena, B. Bates, L. R. Cherney, S. C. Cramer, F. Deruyter, J. J. Eng, B. Fisher, R. L. Harvey, C. E. Lang, M. MacKay-Lyons, K. J. Ottenbacher, S. Pugh, M. J. Reeves, L. G. Richards, W. Stiers, R. D. Zorowitz, Council on Cardiovascular American Heart Association Stroke Council, Council on Clinical Cardiology Stroke Nursing, Care Council on Quality of, and Research Outcomes (2016). Guidelines for Adult Stroke Rehabilitation and Recovery: A Guideline for Healthcare Professionals From the American Heart Association/American Stroke Association. Stroke, 47, e98-e169.

Wolf, S. L., Catlin, P. A., et al. (2001). Assessing Wolf motor function test as outcome measure for research in patients after stroke. Stroke, 32, 1635-1639.

Wolf, T.J., & D. M. Nilsen (2015). Occupational therapy practice guidelines for adults with stroke. Bethesda, MD: American Occupational Therapy Association.

Yang, N. Y., D. Zhou, R. C. Chung, C. W. Li-Tsang, and K. N. Fong (2013). Rehabilitation Interventions for Unilateral Neglect after Stroke: A Systematic Review from 1997 through 2012. Frontiers in Human Neuroscience, 7, 187.

Yelnik, A. P., A. Schnitzler, P. Pradat-Diehl, J. Sengler, J. P. Devailly, P. Dehail, C. D'Anjou M, and G. Rode. (2011). Physical and rehabilitation medicine (PRM) care pathways: "stroke patients". Ann Phys Rehabil Med, 54, 506-18.

Statistical Analysis Plan

Data on four key areas of feasibility will be analyzed using descriptive statistics, including measures of frequency, central tendency, dispersion and variation. **See Table 1.**

Key Area	Question	Analysis on Outcome of Interest
Acceptability	
 Do left brain stroke patients view PAT as a satisfactory and credible tool for rehabilitation? 	
 Range of post-PAT satisfaction ratings on CSQ-8 Range of credibility and expectancy ratings on CEQ
Implementation	
 Can KF-NAP®, WMFT, DVPRS and PAT be implemented as planned in left brain stroke patients? 	
 Completion rate for KF-NAP®, WMFT, DVPRS and full 10-session PAT
Adaptation	
 What modifications are necessary for implementation of KF-NAP®, WMFT and PAT in left brain stroke patients? Is classification of lesion location from the medical record consistent with classification using brain mapping? 	
 Number and type of modifications to KF-NAP®, WMFT and PAT protocol Percent agreement on presence or absence of frontal lesion between radiology report and brain mapping
Limited Efficacy Testing	
 Is there promise for application of PAT in left brain stroke patients? 	
 Spatial-motor-sensory and functional assessments over 7 weeks to detect presence of a treatment signal

Table 1. Key areas of feasibility and related data analysis.

Acceptability: We will use the Client Satisfaction Questionnaire (CSQ-8; Atkinson & Zwick, 1982; Larsen et al., 1979) to assess satisfaction and perceived value of PAT. We will use the Credibility/Expectancy Questionnaire (CEQ; Devilly & Borkovec, 2000) to assess the degree to which PAT is believable, convincing and logical (credibility) and the expectations for PAT-induced improvement (expectancy). The CSQ-8 and CEQ have been used in patients with subjective cognitive impairment (Foster et al., 2018).

Implementation: We will record attendance and completion rates to determine whether KF-NAP®, WMFT and PAT can be carried out as planned.

Adaptation: Each session, study staff will complete checklists from the KF-NAP®, the WMFT, and the KF-PAT™ manual (Chen, 2015) to track assessment and treatment fidelity. Notations will be made when modifications to administration methods are required. For the brain mapping, trained raters will map brain lesions using the method from Preliminary Study 4. Then, a blinded neurologist will classify participants as having “frontal” or “nonfrontal” lesions. Using radiology reports, lesions will be classified as “frontal” based on use of that word or “anterior” “premotor” “prefrontal” or “precentral” or as “nonfrontal” if none of those words are present.

Limited Efficacy Testing: To detect the presence of a treatment signal, we will assess spatial-motor-sensory and functional recovery over 7 weeks. We will assess: 1) Functional disability, measured by activities of daily living using the Barthel Index ((Mahoney and Barthel 1965) and cognitive and motor function with the FIM or FONE-FIM; 2) Spatial neglect, measured by the Behavioural Inattention Test-conventional subtest ((Wilson, Cockburn, and Halligan 1987) and CBS via the KF-NAP® (Chen et al. 2012); 3) Motor function, measured by the WMFT (Lin et al., 2009); and 4) Pain, measured by the Defense and Veterans Pain Rating Scale ((Polomano et al. 2016), which includes numbers along with pictures and colors to facilitate nonverbal rating of pain. Assessments will be administered by a trained examiner.

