2.0 Objectives

2.1 Specific Aim 1: To demonstrate the feasibility of adapted PAT procedures in patients with aphasia and memory impairment. Hypothesis: Adapted methods for PAT administration in patients with aphasia are feasible. Even in the presence of memory disorder detecting a treatment signal is possible.

Specific Aim 2: To demonstrate the feasibility of adapted methods for assessing spatial and motor function and pain in patients with aphasia and memory impairment. Hypothesis: Adapted methods for assessing spatial and motor function and pain in patients with aphasia and memory impairment are feasible.

Specific Aim 3: To demonstrate the feasibility of using information about lesion location from the radiology report to classify frontal vs. nonfrontal lesions. Hypothesis: Lesion classification results from radiology reports and brain mapping methods are consistent, confirming this adaptation provides a clinically

accessible, reliable way to identify brain-based predictors of optimal PAT response in future studies.

2.2 Specific Aim 1: Adapted methods for PAT administration in patients with aphasia are feasible. Even in the presence of memory disorder detecting a treatment signal is possible.

Specific Aim 2: Adapted methods for assessing spatial and motor function and pain in patients with aphasia and memory impairment are feasible.

Specific Aim 3: Lesion classification results from radiology reports and brain mapping methods are consistent, confirming this adaptation provides a clinically accessible, reliable way to identify brain-based predictors of optimal PAT response in future studies.

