4.0 Study Endpoints *

4.1 We will assess four key aspects of feasibility of our adapted assessment and treatment procedures: acceptability, implementation, adaptation, and limited efficacy testing (Bowen et al., 2009). See Table 1. Acceptability: We will use the Client Satisfaction Questionnaire (CSQ-8; Attkinson & Zwick, 1982; Larsen et al., 1979) to assess satisfaction and perceived value of PAT. We will use the Credibility/Expectancy Questionnaire (CEQ; Devilly & Borkovec, 2000) to assess the degree to which PAT is believable, convincing and logical (credibility) and the expectations for PAT-induced improvement (expectancy). The CSQ-8 and CEQ have been used in patients with subjective cognitive impairment (Foster et al., 2018). Implementation: We will record attendance and completion rates to determine whether KF-NAP®, WMFT and PAT can be carried out as planned. Adaptation: Each session, study staff will complete checklists from the KF-NAP®, the WMFT, and the KF-PAT™ manual (Chen, 2015) to track assessment and treatment fidelity. Notations will be made when modifications to administration methods are required. For the brain mapping, trained raters will map brain lesions using the method from Preliminary Study 4. Then, a blinded neurologist will classify participants as having “frontal” or “nonfrontal” lesions. Using radiology reports, lesions will be classified as “frontal” based on use of that word or “anterior” “premotor” “prefrontal” or “precentral” or as “nonfrontal” if none of those words are present. Limited Efficacy Testing: To detect the acquisition and maintenance of a treatment signal, we will assess spatial-motor-sensory and functional recovery over 7 weeks (Figure 2). We will assess: 1) Functional disability, measured by activities of daily living using the Barthel Index (Mahoney & Barthel 1965) and cognitive and motor function with the FIM or FONE-FIM; 2) Spatial neglect, measured by the Behavioural Inattention Test-conventional subtest (Wilson et al., 1987) and CBS via the KF-NAP® (Chen et al. 2012); 3) Motor function, measured by the WMFT (Lin et al., 2009); and 4) Pain, measured by the Defense and Veterans Pain Rating Scale (Polomano et al. 2016), which includes numbers along with pictures and colors to facilitate nonverbal rating of pain. Assessments will be administered by a trained examiner.

TABLE 1. Study Endpoints.

Key Area	Aim	Question	Analysis on Outcome of Interest

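### The Aim 3 radiology rule does not require the listed word to describe the left-hemisphere stroke lesion, so other findings in the report can make a nonfrontal left stroke count as frontal

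*Combined protocol and SAP*

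**What the plan says.** The rule appears in the same words in protocol section 4.1 (Adaptation) and in the Adaptation paragraph of the SAP: "Using radiology reports, lesions will be classified as “frontal” based on use of that word or" on use of anterior, premotor, prefrontal or precentral. The other label is the default: "or as “nonfrontal” if none of those words are present". Neither place names a side, an index lesion or a part of the report.

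The comparator has two steps. The first is the mapping itself: "trained raters will map brain lesions using the method from Preliminary Study 4". The label is assigned in the second step, where the plan says that "a blinded neurologist will classify participants as having “frontal” or “nonfrontal” lesions". Again no side or index lesion is stated.

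The outcome in Table 1 is "Percent agreement on presence or absence of frontal lesion between radiology report and brain mapping". It is the only Aim 3 outcome, and no target value is set for it. The Aim 3 hypothesis in section 2.1 reads "Lesion classification results from radiology reports and brain mapping methods are consistent, confirming this adaptation provides a clinically" accessible and reliable means of finding brain-based predictors of response for later studies.

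On eligibility, section 10.2 excludes "History of brain conditions other than left brain stroke, including clinical right brain pathology".

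**The concern.** The rule tests whether a word occurs in the report. It does not test what the word refers to. A radiology report can use the word frontal for things other than the stroke under study, such as atrophy, white matter change, a sinus or a focus in the right hemisphere. If the left stroke is parietal or subcortical, any of these would turn its label to frontal. The issue is a correct word attached to the wrong side or the wrong finding; the choice of words in the list is a separate matter.

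Aim 3 asks whether the report can separate frontal from nonfrontal lesions in people with left brain stroke, and section 3.1 makes this a precondition for patient-selection guidelines. If some labels describe something other than the left stroke, percent agreement mixes two questions: whether the report locates the stroke correctly, and how often reports use a listed word for something else.

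**Working it through.** **Step 1: the texts side by side.** The first half of the rule could be read as applying the words to the stroke lesion, because its grammatical subject is lesions. The default clause does not allow that reading if taken literally, since nonfrontal requires that the listed words be absent. A report on a left parietal stroke that also mentions the frontal sinus contains a listed word, so it cannot be nonfrontal as written.

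The comparator does not settle the matter. Section 3.2 summarises Preliminary Study 4 as trained raters judging from clinical images whether a frontal cortical lesion was present, in patients with right brain stroke. That summary supplies no left-sided limit for this trial.

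**Step 2: what a stray word does to agreement.** There are two branches.

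- The word describes something that mapping would not count, such as a sinus or atrophy, or a right-sided focus that the raters ignore. Only the report label changes, and agreement falls.
- The word describes a right-sided lesion that mapping also counts. Both labels become frontal and agreement does not fall, yet neither label describes the left stroke.

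**Step 3: illustration of the first branch.** The documents state no expected agreement, so there is no figure to reproduce. Inputs:

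- N = 30, the target in section 12.2 ("to achieve the target sample size of 30"), taking every participant to have both labels.
- p, the share whose left stroke is truly frontal. Assumed, 30% to 70%.
- q, the share of nonfrontal left strokes whose report uses a listed word for something else. Assumed, 10% to 40%.
- Mapping is limited to the left stroke lesion, and both methods are otherwise perfect. Assumed.

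The labels agree for all truly frontal strokes (p) and for nonfrontal strokes without a stray word, (1 − p)(1 − q). Hence:

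- Agreement = p + (1 − p)(1 − q) = 1 − (1 − p)q
- Discordant participants = 30(1 − p)q
- Share of frontal report labels that are correct = p / [p + (1 − p)q]

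| p | q | Agreement | Discordant of 30 | Frontal labels correct |
|---|---|---|---|---|
| 30% | 10% | 93% | 2.1 | 81% |
| 30% | 40% | 72% | 8.4 | 52% |
| 50% | 10% | 95% | 1.5 | 91% |
| 50% | 20% | 90% | 3.0 | 83% |
| 50% | 40% | 80% | 6.0 | 71% |
| 70% | 10% | 97% | 0.9 | 96% |
| 70% | 40% | 88% | 3.6 | 85% |

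Worked line: with p = 0.5 and q = 0.1, agreement = 1 − 0.5 × 0.1 = 0.95, discordant = 30 × 0.05 = 1.5, and correct frontal labels = 0.5 / 0.55 = 0.91.

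**Step 4: the second branch.** Let s be the share of stray-word cases in which mapping counts the same finding. Agreement becomes 1 − (1 − p)q(1 − s). At s = 1 it is 100% whatever q is. With p = 0.5 and q = 0.1, 1.5 of 30 participants would then carry matching labels that do not describe their left stroke. This branch is possible only where the stray word refers to a lesion that raters could map.

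**The case against.** Several points on the other side have force.

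- **The rule speaks of lesions.** Section 2.1 speaks of lesion location, and a sensible reader might apply the words only to the description of the stroke. That is a fair reading of the intent, so mislabelling is possible rather than certain. The default clause still says otherwise, and nothing in the plan chooses between the two readings.
- **Section 10.2 may remove many right-sided lesions.** A reader might infer that it excludes only clinical right brain pathology, so that people with a silent right frontal lesion are eligible. The text does not support this. It excludes a history of any brain condition other than left brain stroke, and clinical right brain pathology is one named case. What remains is that 10.2 does not say whether a silent imaging finding counts as history, or that images are read to apply the criterion. Nor does it help to note that a first stroke is not required: an earlier right stroke falls under the exclusion, and an earlier left frontal stroke is correctly labelled frontal.
- **The mapping method is taken from cited work.** It may restrict side or lesion there. That cannot be judged from the protocol and SAP, so the remark about mapping applies only to the method as summarised in them.
- **Overcalling is partly a property of the method under test.** Aim 3 asks whether a simple, clinically usable rule works. If stray words make it overcall, lower agreement is a legitimate result. This stands, and it is the reason to report the bare word search as well as the restricted rule.
- **Reading in context changes the method.** It brings in some judgement. This also stands, as a cost.

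**Conclusion.** The concern holds in limited form. As written in both places, the rule scores a nonfrontal left stroke as frontal when a listed word describes something else, and neither the mapping summary nor section 10.2 closes the gap. Percent agreement may fall for reasons unrelated to the left stroke, or may stay high while both labels describe another finding.

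The size cannot be determined from the documents, which give neither p nor q. The illustration (95% agreement at p = 50% and q = 10%, 80% at q = 40%) covers only the branch in which mapping ignores the other finding, and its upper end has no documentary basis.

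A reader might go further and infer that percent agreement cannot answer Aim 3 at all. The documents do not support that, because overcalling by the bare rule is itself informative about a clinic-ready method. The branch that agreement cannot reveal is the one in which both methods count the same unrelated lesion; whether it occurs depends on how 10.2 and the mapping method are applied. The change is worth making before any report is classified.

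**What to change.** In protocol section 4.1 and the SAP, replace the condition with text to this effect:

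> A report is classified as frontal only if a listed word describes a left-hemisphere stroke lesion. Words that describe the right hemisphere, or findings other than a stroke lesion (for example white matter change, atrophy or a sinus), do not count. The mapping raters and the neurologist likewise classify left-hemisphere stroke lesions only. Study staff blinded to the mapping result read the reports in context.

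Report percent agreement twice, once for the restricted rule and once for the bare word search, with the number of labels that change between them. The comparison shows how far stray words matter and whether the simpler search would be good enough for clinics.

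The cost is a few sentences in two places and a contextual reading of about 30 reports by existing staff, with slightly more judgement than a mechanical search. No new data are needed.
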